## 2.4 Study Rationale

This study aims to evaluate the impact of inhaled Ampion on mortality and clinical outcomes in adults with severe to critical COVID-19. The data from this study will inform decisions for the clinical development of Ampion.

### 2.4.1 Study Background

COVID-19 infection is associated with pathological findings including pneumonia and inflammation of lung tissue. The triggering insult to the tissue has been associated with a hyper innate inflammatory response in which cytokines and related proteins, such as tumor necrosis factor alpha (TNF $\alpha$ ), are excessively increased with the severity of COVID-19 and respiratory failure. This inflammatory response commonly results in ALI or its more severe form, ARDS, in which leads to pulmonary edema and fibrosis with poor prognosis. ALI/ARDS is believed to be a major cause of mortality in COVID-19 patients.

*In vitro* nonclinical studies show Ampion modulates cytokine levels in various immune cell models where it decreases the levels of inflammatory cytokines, including TNF $\alpha$ . Due to its mode of action, Ampion may be a viable treatment option for those infected with COVID-19 in effort to improve clinical outcomes, slow the progression and severity with associated critical COVID-19 inflammatory conditions (e.g., progression to respiratory failure, the need for assisted breathing, and ultimately mortality) (Thomas, 2020).

This study evaluates the safety and the efficacy of inhaled Ampion treatment for COVID-19 patients with respiratory distress.

### 2.4.2 Preclinical Data

The intravenous administration of the sole starting material of Ampion, HSA, has exposed humans, including critically ill patients and those with compromised respiration with ALI and ARDS (HSA prescribing information; Farag, 2016; Polito 2013), to the components in Ampion with no remarkable safety concerns.

The potential for local toxicity of Ampion has been evaluated in an *in vivo* preclinical study using the inhaled route of administration. In *in vivo* toxicity study FY20-121, there were no clinical signs observed that were considered related to treatment with Ampion. There were no treatment-related effects on body weight or food consumption during the treatment period. There were no treatment-related changes in hematology, clinical biochemistry or respiratory tract histopathology that could be attributed to treatment with Ampion. The inhalation exposure of Ampion at the highest dose for 5 days was well tolerated and produced no apparent changes in any of the parameters evaluated. The maximum feasible dose achieved in the study was established as the no observable adverse effect level (NOAEL), which corresponded to approximately 15 times the proposed clinical dose of Ampion in this study.

The Ampion preclinical testing program is designed to support clinical development for the treatment of inflammatory diseases and the dysregulation of proteins responsible for

modulating the immune response. COVID-19 infection is associated with a hyper innate inflammatory response, where increased levels of cytokines and related proteins (e.g., TNF $\alpha$ ) are correlated with the severity of COVID-19 illness (Del Valle 2020; Yang 2017; Channappanavar 2017).

Preclinical pharmacology studies of Ampion using human *in vitro* models of immunology (e.g., peripheral blood mononuclear cells and macrophages) indicate that Ampion reduces inflammatory cytokines (e.g., TNF $\alpha$ ) responsible for the inflammation and tissue damage initiated by viral diseases like COVID-19 (Channappanavar, 2017) and in respiratory distress syndromes (Yang, 2017), while promoting the production of prostaglandins responsible for resolving inflammation in respiratory disease (Loynes 2018).

#### **2.4.3 Dosing Rationale**

The proposed daily dose of 32 mL of Ampion delivered via inhalation is based on Ampion's *in vitro* effect to reduce cytokine (TNF $\alpha$ ) combined with results from *vivo* safety study and experience from the Phase I study AP-014. Nebulized Ampion will be administered via inhalation as an 8 mL dose, four times per day (q.i.d), every 6 hours (q6) for a total daily dose of 32 mL. This treatment regimen is repeated for 5 days. The dosing uses a dose of Ampion that may provide a positive clinical outcome while minimizing safety risks.

### **2.5 Benefit and Risk Assessment**

Patients with respiratory distress due to COVID-19 may be at a high risk of progressing to life-threatening, critical disease. Ampion may provide a safe and effective treatment option for these patients.

The anticipated risks of inhaled Ampion treatment are considered low and are based on preclinical safety studies, inhalation use in COVID-19 patients, IV use in COVID-19 patients, intra-articular use for another indication (osteoarthritis), and decades of use of the sole starting material of the product, IV HSA, in severely ill patients. Theoretical risks come from historical use of IV HSA, including rare allergic reactions and facial flushing. The product is a derivative of human plasma, however based on effective donor screening and product manufacturing processes, it carries an extremely remote risk for transmission of viral diseases. A theoretical risk for transmission of Creutzfeldt-Jakob Disease (CJD) also is considered extremely remote. No cases of transmission of viral diseases or CJD have been identified for 5% HSA or Ampion.

As an immunomodulatory drug, Ampion may interrupt the inflammation responsible for respiratory complications for COVID-19 patients, which could improve clinical outcomes.

### 3 STUDY DESIGN

#### 3.1 Study Design Overview

This is a Phase II randomized, double-blinded, placebo-controlled study to evaluate the safety and efficacy of inhaled Ampion in participants with respiratory distress due to COVID-19.

Interested COVID-19 patients will sign the appropriate informed consent document(s) prior to completion of any procedures. The investigator will review inclusion and exclusion criteria prior to any invasive procedures. If the patient is eligible after this review, the site will perform the necessary, if any, study procedures to confirm eligibility.

Participants will be randomized 1:1 to active or placebo using a random allocation sequence stratified by disease severity. The general sequence of events during the treatment and assessment period:

- Complete baseline procedures and sample collection.
- Participants are randomized to Ampion or placebo.
- Participants receive study intervention (active or placebo) inhaled via nebulization for 5 days.
- Complete safety monitoring, study procedures, and sample collection through Day 60.

All subjects receiving test product will also receive the standard of care (SOC) for COVID-19, which may include:

- Oxygen administration to maintain oxygen saturation of 90% or greater, including the use of supplemental oxygen, NIV, and mechanical ventilation circuits.
- Nursing physical that may include review of neurological; pulmonary; cardiac; gastrointestinal; and urinary assessment at least daily during treatment.
- Vital monitoring (heart rate, blood pressure, temperature, respiratory rate, SpO2) at least daily during treatment.
- Telemetry monitoring to evaluate heart rhythm and rate.
- Diet as tolerated to satisfy nutritional needs.
- Treatments for COVID-19 symptoms including antibiotics, cough suppressants/expectorants, anti-coagulants, fever reducers/pain killers, anti-nausea drugs, and/or bronchodilators.
- Treatments for COVID-19 as approved by the FDA including expanded access, emergency, or compassionate use (i.e., remdesivir, dexamethasone, convalescent plasma).
- Medications will be recorded as concomitant medication, tabulated, and compared among groups.

The clinical effects, safety, and tolerability of treatment will be evaluated from baseline through Day 60. Evaluations at screening and during the 5-day treatment occur in person. Evaluations after the 5-day treatment to the end of the study (days 7 to 60) will typically occur via telephone contact unless the patient is in an inpatient setting.

## 3.2 Study Objectives

### 3.2.1 Primary Objective

The progression to mechanical ventilation or death has been lower than observed earlier in the pandemic. Based on the changing impact of COVID-19, the primary trial objective is to evaluate the effect of Ampion on clinical improvement in adult participants with respiratory distress due to COVID-19.

### 3.2.2 Secondary Objectives

The secondary trial objectives evaluate the safety and efficacy of inhaled Ampion versus control in improving the clinical course and outcomes of participants with respiratory distress due to COVID-19.

## 3.3 Study Endpoints

### 3.3.1 Primary Endpoint

The primary endpoint assesses the effect of Ampion compared to placebo on clinical improvement. Clinical improvement is measured as the change in ordinal scale from baseline through Day 5 and Day 28.

### 3.3.2 Secondary Endpoints

Secondary endpoints assess the effect of inhaled Ampion treatment compared to placebo on the clinical outcomes for participants with respiratory distress due to COVID-19 as follows:

Objective	Endpoint
Secondary	
Assess the effect of Ampion compared to placebo on safety	

Incidence of adverse events (AEs) and serious adverse events (SAEs) from baseline to Day 60.

Assess the effect of Ampion compared to placebo on clinical health	

Change in NEWS2 score from baseline through Day 5.

Change in NEWS2 score from baseline to hospital discharge.

Assess the effect of Ampion compared to placebo on hospital stay	

Hospital length of stay (LOS) from admission to discharge.

Assess the effect of Ampion compared to placebo on oxygen use	

Change in baseline in oxygen use, blood oxygen saturation, and oxygen flow rate from baseline through Day 5.

Assess the effect of Ampion compared to placebo on progression to respiratory failure	

Percentage of participants who progress to respiratory failure (i.e., need for mechanical ventilation, ECMO, non-invasive ventilation) by Day 28.

Assess the effect of Ampion compared to placebo on intensive care	

Percentage of participants who require Intensive Care Unit (ICU) admission by Day 28.

ICU-free days through Day 28.

ICU LOS from ICU admission to discharge.

Assess the effect of Ampion compared to placebo on all-cause mortality	

Percentage of participants with a successful outcome (life) or unsuccessful outcome (death) by Day 28.

### 3.3.1 Exploratory Endpoints

Exploratory endpoints assess the effect of inhaled Ampion treatment compared to placebo on the clinical outcomes for participants with respiratory distress due to COVID-19 as follows:

Objective	Endpoint
Exploratory	
Assess the effect of Ampion compared to placebo cytokine profile	

Modulation of cytokine levels from baseline to Day 5.

### 3.4 Blinding and Randomization

The treatment in this study will be blinded to the subjects, investigators, any individual conducting the study (e.g., nursing and pharmacy staff) and clinical study personnel. Participants will be assigned to treatment by a randomization schedule developed and maintained by an independent statistician.

Participants are randomized to active treatment or control, following an equal allocation to treatment arms, stratified by COVID-19 disease severity (severe or critical as defined in [Section 4.4](#)).

Study drug and placebo will be provided as blinded investigational product (IP) with appropriate labeling to link to the randomization code. Where required, safety personnel and/or investigator may be unblinded to a particular subject's treatment assignment to meet reporting requirements to Regulators.

A data management plan and statistical analysis plan will be approved by the sponsor prior to unblinding study data.

### 3.5 Data Safety Monitoring Board

A Data Safety Monitoring Board (DSMB) will be established to review the safety of inhaled Ampion as the study progresses. The DSMB will be primarily responsible for reviewing any serious Adverse Event (SAE) and other clinically important safety findings (e.g., discontinuations due to AEs) that may occur during the study.

### 3.6 Stopping rules

The entire study may be stopped under defined circumstances as outlined in [Section 6](#).

## 4 SELECTION OF PARTICIPANTS

### 4.1 Number of Participants

The trial is designed for approximately 200 patients across two treatment arms (active or control), with a 100 subjects per arm, randomized 1:1 using a random allocation sequence stratified by COVID-19 disease severity (severe or critical).

The number of participants is selected based on the effects observed for the primary endpoint, all-cause mortality. A study in the New England Journal of Medicine with over 4,000 patients receiving the standard of care (SOC) for COVID-19 found a 26% mortality rate at Day 28 (njem 384;8, February 25, 2021). There was a similar observation in the Ampion Phase I study (AP-014) for patients with respiratory distress due to COVID-19 with a mortality for the SOC control arm of 21% by Day 28. In the AP-014 study, a lower mortality rate (8%) was observed for subjects receiving inhaled Ampion. Assuming the same proportions of deaths (8% for Ampion and 26% for control) by Day 28, the number of subjects (n=200) achieves at least an 80% power.

### 4.2 Recruitment Methods

Subjects will be recruited from the population being seen by Investigators at the clinical sites participating in the study.

### 4.3 Participant Characteristics

The participant population are those infected with SARS-CoV-2 that have developed respiratory distress due to COVID-19 and are progressing towards respiratory failure. These patients have the signs and symptoms indicative of severe COVID-19 and critical COVID-19. Treatment of COVID-19 depends on the stage and severity of disease with a hyperinflammatory state observed in the moderate to severe stages that are thought to lead to clinical complications and critical COVID-19 (Gandhi 2020). Treatment with immunomodulators at this point in the disease may be more effective than anti-viral treatments.

The population of participants with respiratory distress due to COVID-19 who show the signs and symptoms of severe or critical COVID-19 were selected for this study to evaluate the efficacy of Ampion as an immunomodulatory therapy that may improve the clinical outcomes of the disease and may reduce mortality.

#### 4.4 Inclusion Criteria

Patients should fulfill all the following inclusion criteria:

1. Male or female,  $\geq 18$  years old.
2. Diagnosed with COVID-19, as confirmed using a standard RT-PCT assay or an equivalent test.
3. Baseline severity categorization of severe or critical COVID-19 infection per FDA Guidance for developing drugs and biological products for COVID-19 (February 2021):
  - a) Severe COVID-19:
    - Symptoms suggestive of severe systemic illness with COVID-19, which could include shortness of breath or respiratory distress
    - Clinical signs indicative of severe systemic illness with COVID-19, such as respiratory rate  $\geq 30$  per minute, heart rate  $\geq 125$  per minute, SpO2  $\leq 93\%$  on room air or PaO2/FiO2  $\leq 300$
  - b) Critical COVID-19:
    - Oxygen delivered by high-flow nasal cannula (heated, humidified, oxygen delivered via reinforced cannula at flow rates  $> 20$  L/min with fraction of oxygen  $\geq 0.5$ ) or
    - Non-invasive mechanical or endotracheal mechanical ventilation
4. Informed consent obtained from the patient or the patient's legal representative.

#### 4.5 Exclusion Criteria

Patients fulfilling one or more of the following criteria may not be enrolled in the study:

1. As a result of the medical review and screening investigation, the Principal Investigator considers the patient unfit for the study and/or progression to death is imminent and inevitable irrespective of the provision of treatments.
2. Clinical diagnosis of respiratory failure requiring ECMO and/or therapy is not available due to resource limitation.
3. Shock defined by systolic blood pressure  $< 90$  mm Hg, or diastolic blood pressure  $< 60$  mm Hg or requiring vasopressors.
4. Multi-organ dysfunction/failure.
5. Patient has severe chronic obstructive or restrictive pulmonary disease (COPD) (as defined by prior pulmonary function tests), chronic renal failure, or significant liver abnormality (e.g., cirrhosis, transplant, etc.).
6. Patient has chronic conditions requiring chemotherapy or immunosuppressive medication.
7. A history of allergic reactions to human albumin (reaction to non-human albumin such as egg albumin is not an exclusion criterion) or ingredients in 5% human albumin (N-acetyltryptophan, sodium caprylate).
8. Prolonged QT interval.
9. Patient has known pregnancy or is currently breastfeeding.
10. Patient planning to become pregnant, or father a child, during the treatment and follow-up period and/or is not willing to remain abstinent or use contraception.

11. Participation in another clinical trial (not including treatments for COVID-19 as approved by the FDA through expanded access, emergency, or compassionate use), or participation in a trial such that enrollment in this study would fall within the time frame of the half-life of the other investigational product(s).

#### **4.6 Inclusion of Patients Incapable of Giving Informed Consent**

Patients who are not sedated or otherwise cognitively impaired may be capable of giving informed consent. In the remaining cases, patients will be enrolled in the study via their legally authorized representative (LAR) by telephone or in person. Enrolled via LAR by telephone requires confirmation of enrollment by two clinicians (e.g., registered nurse or physician).

## 5 STUDY PLAN, PROCEDURES, AND ASSESSMENTS

### 5.1 Description of Study Visits

The mortality, clinical effects, safety, and tolerability of treatment will be evaluated from baseline through Day 60. Evaluations at screening and during the 5-day treatment occur in person. Evaluations after the 5-day treatment to the end of the study (days 6 to 60) will typically occur via telephone. The Schedule of Assessments is shown in [Section 1.2](#).

#### 5.1.1 Screening (-3 Days to Day 1)

The following procedures will be performed at Screening:

- Evaluate all inclusion and exclusion criteria to ensure that patients meet all inclusion criteria and none of the exclusion criteria.
- Medical history, pre-existing conditions, and comorbidities. Include the symptom onset date for COVID-19 symptoms and date of COVID-19 test.
- Diphenhydramine, hydroxychloroquine, and azithromycin all prolong the cardiac QT interval, increasing risk of fatal cardiac arrhythmia. Therefore, severely-ill subjects receiving multiple drugs that prolong QT intervals will be reviewed carefully by the P.I. on a case-by-case adjudication for benefit-risk ratio and close cardiovascular monitoring. Note, subjects who have baseline QT prolongation are excluded from this study.
- Perform pregnancy test, as applicable
- Obtain informed consent before the starting any study specific procedures.

#### 5.1.2 Baseline (Day 1 Prior to Treatment)

The following procedures will be performed at Baseline (first assessment prior to treatment):

- Confirm eligibility (review inclusion/exclusion criteria).
- Randomize patient to study arm.
- Demographics (age, sex, race, height and weight)
- Concomitant medications/therapies
- Vital signs: heart rate, systolic and diastolic BP, body temperature, respiratory rate.
- SpO2 and supplementation oxygen mode/flow rate
- ECG monitoring (telemetry) or 12-lead ECG: record aberrant changes in waves/intervals
- Hematology, biochemistry tests
- Cytokine and chemokine assays
- Ordinal scale and NEWS2 assessments
- Aes

#### 5.1.3 Treatment Period (Day 1 to Day 5)

The following procedures will be performed during the Treatment Period (Day 1 to Day 5) while subject is hospitalized for the index hospitalization:

- Begin inhalation treatment of study intervention (active or placebo) daily within 6 hours of randomization.
- Concomitant medications/therapies

- Vital signs: heart rate, systolic and diastolic BP, body temperature, respiratory rate
- SpO2 and supplementation oxygen mode/flow rate
- ECG monitoring (telemetry) or 12-lead ECG: record aberrant changes in waves/ intervals.
- Hematology, biochemistry tests – these tests are performed at baseline and every other day through treatment and through hospital.
- Cytokine and chemokine assays – these tests are performed at baseline and at Day 5.
- Ordinal scale and NEWS2 assessments
- Aes

#### **5.1.4 Hospitalization Period, as applicable (Day 6 through hospital discharge)**

Hospitalization refers to hospital and/or in-patient settings. The following procedures will be performed for the remainder of the hospitalization, as applicable:

- Concomitant medications/therapies
- Vital signs: heart rate, systolic and diastolic BP, body temperature, respiratory rate
- SpO2 and supplementation oxygen mode/flow rate
- ECG monitoring (telemetry) or 12-lead ECG: record aberrant changes in waves/ intervals – monitored as needed for patients who have abnormal readings or events requiring measurements.
- Hematology, biochemistry tests – these tests are performed at baseline and every other day through treatment and through hospital stay. In the case of a clinically significant abnormal lab result, continue to collect and test those samples to resolution and/or discharge, whichever should occur first.
- Cytokine and chemokine assays – these tests are performed at hospital discharge.
- Ordinal scale and NEWS2 assessments
- Aes

#### **5.1.5 Post-Treatment Follow-Up (Days 28, 60)**

The following procedures will be performed at all follow-up visits (Days 28, 60):

- Mortality
- Concomitant medications/therapies
- Hospital LOS
- ICU LOS
- Ordinal scale and NEWS2 assessments
- Aes

## 5.2 Assessment Methods

### Demographic Data

Demographic data will be collected from medical records: age, gender, race, height and weight, comorbidities.

### Medical History

Medical history and pre-existing conditions will be collected from medical records.

### Concomitant Medications

Concomitant medications will be collected from the medical records: prior (pre-hospitalization) concomitant medications, in-patient concomitant medications.

### Mortality

All-cause mortality will be recorded at hospital discharge, Days 28 and 60, as applicable. Cause of mortality will be assessed and documented. All-cause mortality is calculated for the primary endpoint as the percentage of participants with a successful outcome (life) or unsuccessful outcome (death).

### Length of Stay (LOS)

Due to the COVID-19 health emergency, the Centers for Medicare and Medicaid is temporarily allowing long-term care facilities not normally used as a resident's room to accommodate beds and residents for care in emergencies/situations needed to help with surge capacity. Therefore, hospitalization refers to hospital and/or inpatient care during the COVID-19 health emergency. Inpatient care may include hospitals treating COVID-19 patients; dedicated COVID-19 treatment facilities with 24/7 care; and/or dedicated research facilities with 24/7 care.

Dates of hospitalization and ICU admission as well as discharge dates will be recorded at hospital discharge, Days 28 and 60, as applicable. Hospital discharge will be clinically indicated as the time when patients no longer require 'in hospital' and/or 'in patient' care in the hospital and/or inpatient care unit. A patient will be considered 'moved out of the ICU' when they are transitioned and/or stepped down from the ICU. Patients will be defined as "stepdown" by exclusion (i.e., that they no longer meet any criteria for full intensive care). These patients may still require frequent monitoring and/or nursing care and may also have some minimal organ support requirement but no longer remain in the ICU (Prin, 2014).

The hospital LOS and ICU LOS will be calculated as follows:

- ICU admission: defined (in days) as the first study day when ICU status is changed to "yes" minus baseline date + 1
- Hospital LOS: is defined (in days) as the date of hospital discharge minus date of hospital admission + 1
- ICU LOS: defined (in days) as the date moved out of ICU minus first study date when ICU admission changed to "yes" + 1

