### 7.1 Dosing and Administration of Study Medication

Ampion treatment will be provided as a solution in glass vials ready for human use and treatment administration. Appropriately trained site personnel will administer the study treatment.

Participants will receive a daily dose (32 mL/day) of study intervention (active or placebo) through nebulized inhalation delivered in four equally divided doses of 8 mL, every 6 hours (q\_6), for 5 days. Treatment should commence within 6 hours of randomization. Treatment should terminate at the end of the 5-day treatment period, or when a patient is discharged, whichever comes first.

As outlined in [Section 2.1](#), Ampion or placebo will be delivered in nebulized form to patients using the Aeroneb® Solo Nebulizer System (manufacturer Aerogen Limited, Galway, Ireland), which consists of the Aerogen® Pro-X Controller and the Aerogen® Solo adaptor. Study intervention (active or placebo) aerosolized using the Aeroneb® Solo Nebulizer will be delivered *via* an appropriate aerosol delivery assembly for inhaled drug administration as clinically indicated, *e.g.*, using the hand-held Aerogen Ultra, NIV, and/or a mechanically ventilated circuit. The aerosol delivery assembly used to deliver aerosolized Ampion to each patient will be determined at the treating physician's discretion based on the severity of respiratory illness and clinical needs of the patient at enrolment and continuing throughout the study. Appropriate settings for aerosol delivery assembly respiratory parameters (*e.g.*, supplemental O2 content, flow rate, inspiratory/expiratory pressure, etc.) will be determined for each patient by the treating physician on an ongoing basis as clinically indicated.

Participants will be monitored for any respiratory and/or cardiac distress via vital sign monitoring including respiratory rate, heart rate, and blood pressure daily throughout the study product treatment period.

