4.3 Hospital Stay

Hospital stay is measured by hospital length of stay (LOS) from admission to discharge.

The hypotheses to be tested are:

$$H_0: \text{Median}_A = \text{Median}_S \text{ versus } H_A: \text{Median}_A \neq \text{Median}_S$$

Where Median_A and Median_S are the median hospital length of stay for the Ampion and placebo groups. Assuming there is no censoring, this will be tested using the Wilcoxon rank sum test via PROC NPAR1WAY. If censoring occurs, e.g., death, then the log rank test will be used based on PROC LIFETEST.

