4.5 Progression to Respiratory Failure

Progression to respiratory failure is measured as the percentage of participants who progress to respiratory failure (i.e., need for mechanical ventilation, ECMO, non-invasive ventilation) by Day

The hypotheses to be tested are:

$$H_0: \pi_A = \pi_S \text{ versus } H_A: \pi_A \neq \pi_S$$

Let π_A and π_S represent the proportion of patients who have respiratory failure for Ampion and control during the first 28 days after randomization. This difference will be tested utilizing the appropriate chi-square test or Fisher's exact test utilizing PROC FREQ with the EXACT option, if needed. Also, the median time to respiratory failure will be tested for difference between the two groups via the log-rank test. The log-rank test will be performed using PROC LIFETEST; and the estimation of the time-to-event distributions will be performed using the method of Kaplan and Meier.

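### Hospital length of stay is counted from admission, so values can include days before randomisation; this costs precision on one secondary endpoint but causes no bias

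*Protocol*

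**What the plan says.** The Length of Stay part of Protocol 5.2 gives the definition: "Hospital LOS: is defined (in days) as the date of hospital discharge minus date of hospital admission + 1". The endpoint tables in both documents describe the endpoint as running from admission to discharge, and SAP 4.3 repeats it: "Hospital stay is measured by hospital length of stay (LOS) from admission to discharge".

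Other time measures start inside the trial. In the same part of Protocol 5.2, time to ICU admission is counted from the baseline date, and ICU stay is the "date moved out of ICU minus first study date when ICU admission changed to" yes, plus one day. SAP 4.5 counts respiratory failure "during the first 28 days after randomization".

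On when patients enter:
- Screening may start on Day -3 (Protocol 1.2 and 5.1.1).
- Protocol 4.4 and 4.5 set no limit on days in hospital before randomisation. The critical stratum includes patients on "Non-invasive mechanical or endotracheal mechanical ventilation".
- Protocol 7.1 says: "Treatment should commence within 6 hours of randomization". Randomisation is therefore close to the start of exposure.

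On the test, Protocol 9.4.2 and the general text of SAP Section 4 name a two-sample t-test for length of stay. SAP 4.3 names the Wilcoxon rank-sum test, or the log-rank test if there is censoring, with death as its example. Neither document plans a stay counted from randomisation, an adjustment for prior days or a sensitivity analysis on this point.

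**The concern.** Days in hospital before randomisation cannot respond to treatment, yet they count in the outcome. Take two patients who are both discharged on Day 8. One was admitted on the day of randomisation and scores 8. The other had already been in hospital for 10 days and scores 18. Their stay under treatment is identical.

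What is at stake is precision. Variation in prior stay adds to the variance of the outcome and carries no information about the drug.

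The log-rank option raises a further point. Measured from admission, each patient enters the risk set at admission. Yet nobody who was later enrolled could have been discharged before randomisation. The risk sets therefore contain person-days on which the event was impossible. That option may well be the one used, because SAP 2.4 sizes the trial on 8% and 26% mortality and SAP 4.3 treats death as censoring.

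**Working it through.** **The plan's own power figure.** The only power statement is for Day 28 mortality: 26% v 8%, n = 200, at least 80%. With 100 per arm and two-sided alpha 0.05:
- standard error under the null: √(2 × 0.17 × 0.83 / 100) = 0.0531
- standard error under the alternative: √((0.26 × 0.74 + 0.08 × 0.92) / 100) = 0.0516
- z = (0.18 − 1.96 × 0.0531) / 0.0516 = 1.47, so power is about 92.9% (92.6% at alpha 0.047)

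The statement is met, but it says nothing about length of stay.

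**Inputs for length of stay.** From the documents: 100 per arm, two-sided tests, final alpha 0.047 (SAP 7.1), and Phase I mean stays of 7 v 11 days (Protocol 2.3). Not in the documents, so assumed: the SD of stay after randomisation, the distribution of prior stay, and the correlation between the two.

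**Normal approximation (mean comparison).** Prior days leave the expected difference unchanged and alter only the SD:

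SD from admission = √(SD_post² + SD_pre² + 2ρ·SD_post·SD_pre)

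With SD_post = 7 and ρ = 0:

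| SD of prior days | SD from admission | Power, difference 3 days | Power, difference 4 days (Phase I) |
|---|---|---|---|
| 0 (from randomisation) | 7.00 | 85.2% | 98.0% |
| 1 | 7.07 | 84.5% | 97.8% |
| 2 | 7.28 | 82.3% | 97.1% |
| 3 | 7.62 | 78.8% | 95.8% |
| 5 | 8.60 | 68.4% | 90.3% |

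The correlation matters. For a difference of 3 days and a prior SD of 2:
- ρ = −0.3: SD = √(49 + 4 − 8.4) = 6.68, power 88.3%, so no loss
- ρ = +0.3: SD = √(49 + 4 + 8.4) = 7.84, power 76.5%

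**Simulation of the Wilcoxon test.** Lognormal stay after randomisation, independent gamma prior days with mean equal to SD, whole days, no deaths, alpha 0.047:

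| Mean prior stay (days) | 7 v 9.5 days (assumed SD 6 and 7.5) | 7 v 11 days (assumed SD 6 and 8.5) |
|---|---|---|
| Counted from randomisation | 88–91% | over 99% |
| 1 | 87% | 99% |
| 2 | 82% | 99% |
| 3 | 77% | 98% |
| 5 | 64% | 91–94% across runs |

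**Log-rank test, no deaths.** For 7 v 9.5 days, power falls from about 76–77% to 73%, 65% and 49% at mean prior stays of 2, 3 and 5 days.

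**No treatment effect (9 v 9 days).** Over three assumed patterns of prior stay, the t-test and Wilcoxon test rejected in 4.0% to 5.6% of 2,000 trials, whichever origin was used. The log-rank test from admission rejected in 5.0% to 6.2% of 600 trials, which is within simulation error of 4.7%.

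**The case against.** Admission to discharge is a legitimate measure of total hospital burden. It is used consistently in both documents and is the natural match to the Phase I length of stay. At the Phase I effect, the Wilcoxon loss is only about 0 to 2 points up to a mean prior stay of 3 days. All of that stands, and it limits the size of the point. Two cautions apply: the Phase I result comes from 27 patients, so the true effect may be smaller, and power is more sensitive at smaller effects.

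A reader might infer four stronger things that the documents do not support:
- **That every value contains pre-treatment days.** A patient admitted and randomised on the same day contributes none, and no minimum prior stay is set.
- **That chance imbalance in prior stay is a separate harm.** It is the same added variance, already in the standard error. Stratification by severity may also balance part of it.
- **That lost precision here blocks the later secondary tests.** In the stated order, length of stay is reached only if AE/SAE incidence and both NEWS2 tests succeed first. SAP 9.6 also says that no multiplicity adjustment is made for secondary efficacy analyses, so it is unclear whether the sequence operates as a gate.
- **That hospital stay breaks with every other endpoint.** The contrast with ICU stay is fair. Respiratory failure and ICU admission are tested mainly as Day 28 proportions, so their origin is a weaker comparison.

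**Conclusion.** The point holds as an avoidable loss of precision on one secondary endpoint. The definition is clear in both documents and nothing in them corrects it. It creates no bias in the mean difference and no type I error inflation.

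The size cannot be fixed from the documents. With independent prior days of mean 1 to 5, Wilcoxon power drops by a few points to about a quarter for 7 v 9.5 days, and by about 0 to 6 points for 7 v 11 days (a little more in some runs). The loss is small if nearly everyone is randomised soon after admission. It can vanish if prior and later stay are negatively correlated, and it grows if they are positively correlated. The simulated figures exclude deaths. The risk-set problem under the log-rank option holds whatever the spread of prior stay, although its effect on power depends on that spread.

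**What to change.** In Protocol 5.2, the endpoint tables of both documents, and SAP 3.2 and 4.3, define the tested endpoint as date of hospital discharge minus date of randomisation + 1. Refer to the randomisation date itself (SAP 5.10), because SAP 5.11 and 5.12 do not number study days consistently.

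Changing the origin does not settle how deaths count. State that an in-hospital death is not a discharge, and say how it enters the analysis: for example, kept in the risk set to Day 28, or ranked as the worst outcome.

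Keep admission-to-discharge stay as a descriptive summary by arm.

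The cost is a wording change, since admission, randomisation and discharge dates are already collected. The one downside is that the tested figure is less directly comparable with the Phase I length of stay; the descriptive summary largely covers that.
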